## 11 COMPLIANCE WITH GOOD CLINICAL PRACTICES, ETHICAL CONSIDERATIONS, AND ADMINISTRATIVE ISSUES

The trial will be performed in accordance with ICH Guidelines for Good Clinical Practice (CPMP/ICH/135/95) July 1996 and The Declaration of Helsinki adopted by the 18th World Medical Assembly, in Helsinki, Finland, with later revisions.

Randomization codes will be kept at secure locations accessible by the Investigators and delegated study staff only until the study has finished (last patient has finished treatment and evaluation). If needed the code can be accessed at all times.

## **11.1 Protection of Human Subjects**

### **11.1.1 Subject Informed Consent**

Informed consent/assent must take place before any study specific procedures are initiated. Signed and dated written informed consent must be obtained from each subject and/or from the subject's parent or legal guardian prior to enrollment into the study.

All informed consent/assent forms must be approved for use by the sponsor and receive approval/favorable opinion from an IRB/IEC prior to their use. If the consent form requires revision (e.g., due to a protocol amendment or significant new safety information), it is the investigator's responsibility to ensure that the amended informed consent is reviewed and approved by the sponsor or the designated CRO (IRW) prior to submission to the governing IRB/IEC and that it is read, signed and dated by all subjects subsequently enrolled in the study as well as those currently enrolled in the study.

### **11.1.2 Ethics committee Review and Approval**

Ethics Committee approval as required by ICH-GCP and local regulations will be obtained prior to initiating the study.

## **11.2 Ethical Conduct of the Study**

This study will be conducted in accordance with the ethical principles that originated with the Declaration of Helsinki.

## **11.3 Subject Confidentiality**

All personal study subject data collected and processed for the purposes of this study should be maintained by the investigator and his/her staff with adequate precautions as to ensure that the confidentiality of the data in accordance with local, state, and federal laws and regulations.

Monitors, auditors and other authorized representatives of IRW Consulting, the sponsor, the IRB/IEC approving this study, the FDA, the DHHS, other domestic government agencies, and other foreign regulatory agencies will be granted direct access to the study subject's original medical and study records for verification of the data and/or clinical trial procedures. Access to this information will be permitted to the aforementioned individuals to the extent permitted by law.

A report of the results of this study may be published or sent to the appropriate health authorities in any country in which the investigational product may ultimately be marketed, but the subject's identity will not be disclosed in these documents.

## **11.4 Documentation**

Source documents may include a subject's medical records, hospital charts, clinic charts, electronic records, the investigator's study subject files, as well as the results of diagnostic tests such as OCTs and laboratory tests. The investigator's copy of the Case Report Forms serves as the investigator's record of a subject's study-related data.

### **11.4.1 Retention of Documentation**

All study related correspondence, patient records, consent forms, record of the distribution and use of all investigational products and copies of case report forms should be maintained on file for at least two years after the last approval of a marketing application in an ICH region and until there are no pending or contemplated marketing applications in an ICH region; or until at least two years have elapsed since the formal discontinuation of clinical development of the investigational product. These documents will be retained for a longer period if required by the applicable regulatory requirements or by an agreement with the sponsor. It is the responsibility of the sponsor to inform the investigator/institution as to when these documents no longer need to be retained.

If the responsible investigator retires, relocates, or for other reasons withdraws from the responsibility of keeping study records, custody must be transferred to a person who will accept the responsibility. The sponsor must be notified in writing of the name and address of the new custodian.

All study results will be treated according to rules on confidentiality and anonymity. Domestic law on protection of privacy, procession and destruction of data will be followed. All investigational material will be kept by investigating doctors during the study and with the principal investigator once the study has finished. All study material will be handled with the same confidentiality as other medical records.

## **11.5 Labeling, Packaging, Storage, Accountability, and Return or Disposal of Investigational Product**

### **11.5.1 Labeling/Packaging**

A label will be included describing the appropriate use of the investigational product. The study medication will be packed and labeled according to ICH cGMP guidelines and to local law. This will be performed on behalf of the Sponsor by Oriola, Sweden. The study medication will be packed to avoid inadvertently unmasking and in such a way that the product is protected from deterioration during transport and storage. The labels will be translated as appropriate. The study medication will be filled into single dose vials—the

primary packaging. 10 vials will be packed in one sealed aluminum pouch, the secondary packaging, and then in a tertiary packaging (carton box) per subject.

Each aluminum foil and cardboard box will carry a label with

- Instructions on how to use the eye drops
- Sponsor name and address
- Protocol number
- Number of vials per aluminum pouch or carton box
- Expiry date
- Text regarding clinical trial
- Name and phone number of investigating physician

Both medications, Active and Vehicle, will be packaged in the same type of final packaging to respect the randomization and the masking methodology.

#### **11.5.2 Storage of Investigational Product**

The investigational product must be stored in a secure area accessible only to the investigator and his/her designees. The investigational product will be dispensed only to subjects entered into the clinical study, in accordance with the conditions specified in this protocol.

#### **11.5.3 Accountability of Investigational Product**

The investigational product is to only be prescribed by the principal investigator or his/her named sub investigator(s), and is to only be used in accordance with this protocol.

The investigator must keep an accurate accounting of the investigational product received from the supplier. This includes the amount of investigational product dispensed to subjects, amount of investigational product returned to the investigator by the subjects, and the amount returned or disposed upon the completion of the study. A detailed inventory must be completed for the investigational product.

#### **11.5.4 Return or Disposal of Investigational Product**

At the end of the study, all investigational product will be returned to the sponsor or their designee or destroyed at the study site. The return or disposal of investigational product will be specified in writing.

## **11.6 Recording of Data on Source Documents and Case Reports Forms (CRFs)**

The investigator is responsible for ensuring that study data is completely and accurately recorded on each subject's case report form, source document, and all study-related material. All study data should also be attributable, legible, contemporaneous, and original. Recorded datum should only be corrected in a manner that does not obliterate, destroy, or render illegible the previous entry (eg, by drawing a single line through the incorrect entry and writing the revision next to the corrected data). An individual who has corrected a data entry should make clear who made the correction and when, by adding to the correction his/her initials as well as the date of the correction.

## **11.7 Publications**

The sponsor, Oculis ehf. owns the rights to all data obtained during the conduct of the study and reserves the right to publish all data associated with this clinical study program. Authorship and manuscript composition will reflect cooperation among all parties involved in the study. Authorship will be established before writing the manuscript. The study sponsor, Oculis ehf. will have the final decision regarding the manuscript and publication.

## **12 Toxicology**

In our previous animal studies on dexamethasone suspensions containing cyclodextrin the suspension was well tolerated after topical application to rabbits and no macroscopic signs of irritation and redness were observed (Loftsson et al. 2007; Sigurdsson et al. 2007; Loftsson et al. 2008; Jansook et al. 2010).

Dexamethasone eye drops are already on the market for more than a decade used to treat inflammation in the eyes. We refer to the summary of product characteristics for Maxidex® for list of possible side effects. Most common side effects of Maxidex® are burning in the eyes, increase IOP and ocular discomfort.

To summarize the human use of DexNP eye drops, they have been used in 60 patients treated for up to 12 weeks with up to 6 times a day frequency. No serious adverse effects have been noted. In addition 101 patients received an earlier dexamethasone cyclodextrin eye drops with no adverse effects.

The formulation contains  $\gamma$ -cyclodextrin which has GRAS (generally recognized as safe) recognition in food and drug industry. Cyclodextrins are already used in registered eye preparations e.g. Voltaren Ophtha® from Novartis registered in Sweden and Clorocil® eye drop solution.

Other inactive ingredients of the formulation are commonly used in eye formulations. All of them have an active monograph in the European Pharmacopoeia or USP monograph.

### **13 Disclosure and Confidentiality**

All Unpublished information concerning the test product and research carried out by the Sponsor, including patent applications, manufacturing processes, basic scientific data, etc., is considered confidential and the sole property of the sponsor. Disclosure to third parties must be limited to those undertaking legitimate peer review of the scientific and ethical aspects of the trial and to those participating including the recipients of drugs, so that customary medical care and informed consent can be achieved.

### **14 Insurance Indemnity**

The Sponsor agrees to indemnify (legal and financial coverage) and hold the Investigator free of harm from any claim, whether based on legal principles or on generally accepted liability standards within the pharmaceutical industry, made against him by reason of personal injury, including death, to any person arising out of or connected with the performance of the trial to the extent that the injury is not caused by:

1. failure by the Investigator to adhere to the terms of the Protocol;
2. failure by the Investigator to comply with any applicable governmental regulations;
3. malpractice, negligence or willful malfeasance by the Investigator.

The Investigator agrees to notify the Sponsor and IRW whenever he/she becomes aware of a claim or action, and to co-operate with and to authorize the Sponsor to carry out sole management of such claim or action.

The insurance also covers the Sponsor's liability under law and generally accepted liability standards within the pharmaceutical industry towards any third parties, including subjects, as Sponsor of the trial".

### **15 Trial Agreements**

The Principal Investigator at the investigational site must comply with all the terms, conditions, and obligations of the Clinical Trial Agreement (CTA) for this trial. In the event of any inconsistency between the Trial Protocol and the CTA, the trial agreement shall prevail.

A separate Financial Agreement between /Sponsor/ and the Principal Investigator and/or institution will be filed in the Investigator's File and the Trial Master File.

## **Appendix 1: Schedule of Visits and Measurements**

### Schedule of Visits and Measurements

#### **7 visits over the course of 16 weeks:**

##### Study visit schedule

- Screening Visit (Day -1 to -28)
- Baseline (Day 1)
- Week 2
- Week 4
- Week 8
- Week 12 - Primary end point
- Week 16 - final visit

(visit window is  $\pm$  3 days)

	Visit 1	Visit 2	Visit 3	Visit 4	Visit 5	Visit 6	Visit 7
Procedure	Screening	Day 1	Week 2	Week 4	Week 8	Week 12	Week 16
Informed Consent	X						
Randomisation		X					
Demographic Data		X					
Medical and Ophthalmology History	X	X					
Medication History and Update	X	X	X	X	X	X	X
Visual Acuity	X	X	X	X	X	X	X
Biomicroscopy	X	X	X	X	X	X	X
IOP	X	X	X	X	X	X	X
Ophthalmoscopy	X	X				X	X
OCT	X	X	X	X	X	X	X
Cataract evaluation		X				X	
Blood test	X						X
Blood pressure	X	X	X	X	X	X	X
Urine pregnancy test	X*						
VFQ-25		X				X	
Investigational Product Dispensed		X		X	X		
Investigational Product Returned				X	X	X	
Adverse Events		X	X	X	X	X	X
Exit from Study							X

\*if applicable

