### 5.3 Inclusion Criteria

**Each subject must:**

- a) Have DME of less than 3 years duration since diagnosis with presence of intraretinal and/or subretinal fluid in the study eye, with central

- macular thickness, CMT, of  $\geq 310\mu\text{m}$  by SD-OCT at baseline (Visit 2) (as measured by the Investigator).
- b) Have definite retinal thickening in the study eye due to DME involving the central macula based on the Investigator's clinical evaluation and by SD-OCT; Note: If the DME consists of circumscribed, focal leakage that the evaluating Investigator believes should be treated with laser and no other treatments, the eye is not eligible to be a study eye.
  - c) Have an ETDRS BCVA letter score  $\leq 73$  (Snellen 20/40) and  $\geq 24$  (Snellen 20/320) in the study eye at baseline (Visit 2)
  - d) Have a documented diagnosis of type 1 or type 2 diabetes mellitus and a glycosylated hemoglobin A1c (HbA1c) of  $\leq 12.0\%$  at Visit 1
  - e) Have a negative urine pregnancy test at Visit 1, if female of childbearing potential those who have experienced menarche and who are not surgically sterilized [bilateral tubal ligation, hysterectomy or bilateral oophorectomy] or post-menopausal [12 months after last menses] and must use adequate birth control throughout the study period. Adequate birth control is defined as hormonal – oral, implantable, injectable, or transdermal contraceptives; mechanical – spermicide in conjunction with a barrier such as condom or diaphragm; intrauterine device (IUD); or surgical sterilization of partner. For non- sexually active females, abstinence may be regarded as an adequate method of birth control;
  - f) Agree to not participate in another interventional study after providing informed consent and until the study is completed
  - g) Provide written informed consent prior to any study procedure being performed and be able and willing to follow all instructions and attend all study visits
  - h) Be 18-85 years of age at baseline (Visit 2), of either sex and any race or ethnicity

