#### 8.1.5 Methods for Assignment to Treatment Groups:

At visit 2, the subject will be randomized in a 2:1 ratio to active drug or the vehicle group.

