## **8.8 Study Duration**

16 weeks study duration, preceded by a maximum 4 week screening period.

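### The only planned pregnancy test is at screening, 1 to 28 days before randomisation and first dosing; a urine test at Visit 2 would close the gap cheaply.

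*Combined protocol and SAP*

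**What the plan says.** Appendix 1 lists "Urine pregnancy test" once, with a mark under Visit 1 and a footnote limiting it to applicable subjects. The Visit 2 cell is empty, as are all later ones.

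The eligibility criteria agree. Inclusion 5.3(e) reads "Have a negative urine pregnancy test at Visit 1, if female of childbearing potential", and adds that such women "must use adequate birth control throughout the study period". Exclusion 5.4(gg) covers being pregnant, a positive test at Visit 1, recent pregnancy or breast-feeding, and a planned pregnancy within 9 months of Visit 1. Synopsis criteria e and x say the same.

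On timing, Appendix 1 places Visit 1 between Day -28 and Day -1, and 8.8 gives "16 weeks study duration, preceded by a maximum 4 week screening period". Section 8.1.5 states: "At visit 2, the subject will be randomized in a 2:1 ratio to active drug or the vehicle group". Appendix 1 puts first dispensing at that same visit, Day 1. (Section 5.2 loosely ties randomisation to consent, but 8.1.5 and Appendix 1 are explicit.)

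The haematology and chemistry lists in 6.3 contain no pregnancy test. The text under Optional imaging in 8.3.1 says how a positive test during the study is to be reported and followed up, but schedules no test.

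**The concern.** Exclusion 5.4(gg) has two separate limbs: the state of being pregnant, and a positive result at Visit 1. Section 8.1.4 requires that no exclusion criterion be met at entry. The plan therefore means to keep every pregnant woman out, but gives sites no test for this at the point of entry.

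A conception during screening, or one just before screening and too early for the Visit 1 test, can go undetected. A site that follows the protocol exactly could then randomise and dose a woman whom 5.4(gg) is meant to exclude. Treatment is three drops a day for 12 weeks.

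Exposure may not be purely local. In the earlier randomised trial of these drops in diabetic macular oedema, described in section 1, serum cortisol fell on average by 5.5 from a baseline of 9.7 at week 4, after dosing at the frequency used here. That arm had only 12 patients and the protocol regards the effect as mild. It indicates some systemic activity and is not evidence of fetal harm.

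**Working it through.** No sample size, power or alpha figure is involved. The check is a day count and a comparison of sections.

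**Inputs**
- Visit 1: Day -28 to Day -1 (Appendix 1).
- Visit 2, with randomisation and first dispensing: Day 1 (8.1.5, Appendix 1).
- Maximum screening: 4 weeks (8.8).
- Treatment: 12 weeks (section 4).

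**Age of the test at Visit 2.** With no Day 0, a test on Day -d is d days old on Day 1.
- d = 1 gives 1 day.
- d = 28 gives 28 days, which matches 4 × 7 = 28 from 8.8.

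If a Day 0 is counted, the range becomes 2 to 29 days. If the ±3 day visit window also applied to Visit 2, which the documents do not make clear, the upper end would be 28 + 3 = 31 days.

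**Gain from a Visit 2 test.** Let S be the length of screening in days and L the test's detection lag.
- Visit 1 test only: conceptions later than S + L days before Visit 2 are missed.
- Visit 2 test: only conceptions later than L days before Visit 2 are missed.
- Gain: (S + L) − L = S. The lag cancels, so no value need be assumed.
- S = 1, 7, 14, 21 or 28 gives a gain of 1, 7, 14, 21 or 28 days.

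The interval from last test to first dosing becomes 0 days.

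**How many women?** The documents give neither the number of women of childbearing potential nor a contraceptive failure rate. As an illustration only, assume 2 to 10 such women, 1% to 10% conceptions per woman-year, and the full 28 days:
- Low: 2 × 0.01 × 28/365 = 0.0015 conceptions in the whole trial.
- High: 10 × 0.10 × 28/365 = 0.077.
- On active drug (2:1 randomisation, × 2/3): 0.001 to 0.05.

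This applies rates on contraception throughout. Part of the window gained lies before Visit 1, when the text does not require contraception, so the true figure could be higher.

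**The case against.** The best answer is that this is a design choice with very little at stake. The Synopsis, the criteria and Appendix 1 all agree on Visit 1. Contraception is mandatory, women planning pregnancy are excluded, history is taken again at Visit 2, unscheduled visits are allowed (8.4.2), and 8.3.1 has a pathway for a pregnancy found during the study. The illustrative count is well below one case. All of this stands, and it sets the grade at minor. None of it tests for a pregnancy of which the woman is unaware.

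A second argument is that one Visit 1 test fits the plan's pattern: HbA1c (5.3(d)), the intraocular pressure exclusion (5.4(aa)) and eGFR (5.4(dd)) are also tied to Visit 1. Of the items required at Visit 2, macular thickness (5.3(a)) and BCVA (5.3(c)) need a baseline anyway because they are outcomes. This is fair; blood pressure, checked at both visits (5.4(ee)), is the closest parallel. It shows that the plan already rechecks a safety-type criterion at Visit 2, though not as a general rule.

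Third, the remedy leaves the 84 days of dosing (12 × 7) without a scheduled test, out of up to 28 + 84 = 112 days from the only test to the end of treatment. That is true. The point here is narrower: whether 5.4(gg) is met at entry.

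Finally, the documents give no costs, so calling the change cheap is a judgement. It rests on using a test the trial already uses, at an existing visit, for a subset of subjects.

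**Conclusion.** The point holds as a minor improvement in patient safety. The only planned pregnancy test is 1 to 28 days old at randomisation and first dosing (counting no Day 0), and no other scheduled procedure would reveal an unrecognised pregnancy at that time. A Visit 2 test shortens the untested interval by the length of screening, at most 28 days. A conception too recent to detect at Visit 2 would still be missed. The expected number of women affected is probably very small, but the documents do not allow a firm estimate. Sample size, alpha, power and the efficacy analyses are untouched.

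**What to change.** Make five edits:
1. Appendix 1: mark the urine pregnancy test, if applicable, at Visit 2, to be done before randomisation.
2. Section 5.3(e): require a negative test at Visit 1 and at Visit 2.
3. Synopsis inclusion e: the same.
4. Section 5.4(gg): exclude on a positive test at Visit 1 or Visit 2.
5. Synopsis exclusion x: the same.

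No other change is proposed.

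The running cost is one urine strip per woman of childbearing potential, with no added visit. The administrative cost is a protocol amendment carried to about 13 sites. If it leads to a revised consent form, 11.1.1 requires sponsor or CRO review, submission to the ethics committee, and signing by current as well as new subjects.

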## **Appendix 2: NEI-VFQ-25 questionnaire**

PB/IA

# **National Eye Institute Visual Functioning Questionnaire - 25 (VFQ-25)**

**version 2000**

## **(INTERVIEWER ADMINISTERED FORMAT)**

**January 2000**

RAND hereby grants permission to use the "National Eye Institute Visual Functioning Questionnaire 25 (VFQ-25) July 1996, in accordance with the following conditions which shall be assumed by all to have been agreed to as a consequence of accepting and using this document:

- 1.** Changes to the NEI VFQ-25 - July 1996 may be made without the written permission of RAND. However, all such changes shall be clearly identified as having been made by the recipient.
- 2.** The user of this NEI VFQ-25 - July 1996 accepts full responsibility, and agrees to hold RAND harmless, for the accuracy of any translations of the NEI VFQ-25 Test Version - July 1996 into another language and for any errors, omissions, misinterpretations, or consequences thereof.
- 3.** The user of this NEI VFQ-25 - July 1996 accepts full responsibility, and agrees to hold RAND harmless, for any consequences resulting from the use of the NEI VFQ-25.
- 4.** The user of the NEI VFQ-25 - July 1996 will provide a credit line when printing and distributing this document or in publications of results or analyses based on this instrument acknowledging that it was developed at RAND under the sponsorship of the National Eye Institute.
- 5.** No further written permission is needed for use of this NEI VFQ-25 - July 1996. 7/29/96

© R 1996

